2.10.3. Concomitant Medications Taken During the Follow-up Phase

Follow-up concomitant medications are those that started after the analysis reference end date of the double-blind phase.

3. INTERIM ANALYSIS AND DATA MONITORING COMMITTEE REVIEW

There is no planned interim analysis for this study.

4. SUBJECT INFORMATION

The number of subjects in each analysis set will be summarized and listed by treatment group and overall. In addition, the distribution of subjects by site ID will be presented for the full analysis set.

4.1. Demographics and Baseline Characteristics

Table 2 presents a list of the demographic variables that will be summarized by treatment group and overall for the full analysis set.

Table 2: Demographic Variables

Continuous Variables:	Summary Type
Age (years), calculated based on date of informed consent	Descriptive statistics (N, mean, standard deviation [SD], median and range [minimum and maximum]).
Weight (kg)	
Height (cm)	
Body Mass Index (BMI) (kg/m^2) calculated as $\text{Weight (kg)}/[\text{Height (m)}]^2$	
Waist circumference (cm)	
Categorical Variables	Frequency distribution with the number and percentage of subjects in each category.
Age (18-34 years, 35-54 years, 55-64 years, 65-70 years)	
Sex (male, female, undifferentiated)	
Race ^a (American Indian or Alaska Native, Asian, Black or African American, Native Hawaiian or other Pacific Islander, White, Not Reported, Multiple)	
Ethnicity (Hispanic or Latino, not Hispanic or Latino)	
BMI (underweight $<18.5 \text{ kg}/\text{m}^2$, normal $18.5-<25 \text{ kg}/\text{m}^2$, overweight $25-<30 \text{ kg}/\text{m}^2$, obese $\geq 30 \text{ kg}/\text{m}^2$)	

^aIf multiple race categories are indicated, the Race is recorded as 'Multiple'.

Table 3 presents a list of the psychiatric history variables that will be summarized by treatment group and overall for the full analysis set.

Table 3: Psychiatric History Variables

Continuous Variables:	Summary Type
Age (years) when diagnosed with MDD	Descriptive statistics (N, mean, standard deviation [SD], median and range [minimum and maximum]).
Duration (weeks) of current depressive episode	
Baseline MADRS total score	
Baseline CGI-S score	
Baseline PGI-S score	
Baseline ISI score per eDC	
Categorical Variables	Frequency distribution with the number and percentage of subjects in each category.
Current antidepressant type (SSRI, SNRI)	
Antidepressant treatment history (number of medications with inadequate response taken for at least 4 weeks during the current episode as obtained in the MGH-ATRQ)	
SCID-CT DSM-5 specifiers for MDD (anxious distress, mixed features, melancholic features, atypical features, peripartum onset, seasonal pattern)	
MDD with Anxiety based on HAMA-A (Yes=defined as baseline HAM-A total score ≥ 18 , No=defined as baseline HAM-A total score <18)	
Prior medication use of adjunctive antipsychotics (Yes, No)	
Prior medication use of benzodiazepines (Yes, No)	
Baseline CGI-S score (1=normal [not at all ill]; 2=borderline ill; 3=mildly ill; 4=moderately ill; 5=markedly ill; 6=severely ill; 7=among the most extremely ill patients)	
Baseline PGI-S score (1=none, 2=mild, 3=moderate, 4=severe)	
Baseline ISI score per IWRS (≥ 15 , <15)	

Baseline ISI score per eDC (≥ 15 , < 15) (if different from IWRS)	
Number of major depressive episodes (1, 2, ≥ 3)	
Family history of alcohol abuse (yes, no)	
Family history of anxiety disorder (yes, no)	
Family history of bipolar disorder (yes, no)	
Family history of depression (yes, no)	
Family history of schizophrenia (yes, no)	
Family history of substance abuse (yes, no)	

By-subject listings of the demographic and baseline characteristics as well as general medical history, psychiatric history and tobacco use history will be provided.

4.2. Disposition Information

The number of screen failures will be summarized overall.

The number of subjects in the following disposition categories will be summarized throughout the study by treatment group and overall:

- Subjects randomized
- Subjects receiving study agent
- Subjects who completed the double-blind phase
- Subjects who discontinued from the double-blind phase
 - Reasons for discontinuation from the double-blind phase
- Subjects completing the follow-up phase

Listings of subjects will be provided for the following categories:

- All randomized subjects
- Subjects who discontinued from the double-blind phase
- Subjects who discontinued from the follow-up phase
- Subjects who were unblinded during the study period
- Subjects who were randomized yet did not receive study agent.

These summaries and listings will be provided for the all randomized analysis set.

4.3. Treatment Compliance

4.3.1. Treatment Compliance With Study Agent

Study agent compliance will be summarized descriptively.

Compliance for each subject will be calculated based on the percent of the scheduled number of capsules of study agent actually taken within the double-blind phase. Study agent compliance will be calculated as follows:

Study agent compliance (%) = (actual number of capsules taken/total number of capsules supposed to be taken) x100.

The number of capsules supposed to have been taken will be calculated as the duration of treatment within the phase (i.e., date of last dose of study agent – date of first dose of study agent + 1) multiplied by 2 (since each “dose” of study agent consists of 2 capsules).

Descriptive statistics on the percent (%) compliance will be summarized by treatment group for the safety analysis set. In addition, percent compliance will be categorized as <60%, 60%-<80%, 80%-100%, >100% and the number and percentage of subjects in each category will be summarized.

4.3.2. Treatment Compliance With Baseline SSRI/SNRI Antidepressant

Compliance with baseline SSRI/SNRI antidepressant will be summarized descriptively.

Compliance for each subject will be calculated based on the percent of the scheduled number of days that the baseline SSRI/SNRI antidepressant was actually taken within the double-blind phase. It is defined as:

Compliance with baseline SSRI/SNRI (%) = (number of days baseline SSRI/SNRI antidepressant taken / number of days in double-blind phase)*100.

The number of days in the double-blind phase will be calculated as the duration of double-blind treatment phase (i.e., completion or discontinuation date of the double-blind phase – date of first dose of study drug + 1).

Descriptive statistics on the percent compliance will be summarized by treatment group for the safety analysis set. In addition, percent compliance will be categorized as <60%, 60%-<80%, 80%-100%, >100% and the number and percentage of subjects in each category will be summarized.

4.4. Extent of Exposure

Total duration of exposure (including days off drug) is defined as (date of last dose of study agent – date of first dose of study agent) + 1. Number of doses is defined as the total number of dose administrations. Taking more than 2 tablets within 4 hours is considered as overdose.

Descriptive statistics (N, mean, SD, median, minimum, and maximum) for total duration of exposure (including days off drug) and for number of doses will be presented by treatment group for the safety analysis set.

The mode daily dose will be calculated for each subject, based on days on drug. The lowest mode dose is selected in case of ties. The frequency of mode daily dose will be presented by treatment group.

The mean daily dose of study agent for a subject is calculated as the sum of total daily dose during the treatment phase divided by the total number of days exposed. The final dose is the last non-zero dose received during the double-blind phase. The calculation of mean daily dose and final dose will exclude days off study drug. Descriptive statistics (N, mean, SD, median, minimum and maximum) for mean daily dose and final dose will be presented by treatment group.

A by-subject listing of study drug administration will be provided.

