## TIME AND EVENTS SCHEDULE

Phase	Screening Phase	Double-Blind Treatment Phase a								End-of-Study/Follow-up b
Visit Number	1	2	3	4	5	6	7	8	9	10
Study Day	-28	1	7	14	28	42	84	126	168	182
Study Week	-4	1	1	2	4	6	12	18	24	25-26
Visit Window (days)			±3	±3	±3	±4	±7	±7	±7	7 to 14 days after the last dose
Clinic (C), Phone (P)	C	C	P c	C	C	C	C	C	C	C
Study Proceduresk										
Screening/Administrative Procedures										
Informed consent d	X									
Informed consent for optional genetic research samples	X									
Medical/psychiatric history	X									
Demographic information	X									
Prestudy therapy	X	X								
Preplanned surgery/procedure(s)	X									
Height	X									
Alcohol (breath) test	X	X								
Urine drug test	X									
Urine or blood sample for antidepressant compliance e	X					X				
Inclusion/exclusion criteria f	X	X								
SCID-CT	X									
MGH-ATRQ	X									
ISI	X	X								
Study Drug Administration										
Randomization		X								
Dispense study medication		X		X	X	X	X	X		
Study drug accountability				X	X	X	X	X	X	
Study drug administration g										continuous
Safety Assessments										
Physical examination	X								X	X s
Serum/Urine pregnancy test h Reference source not found.										
Clinical laboratory tests: hematology, serum chemistry, and urinalysis i	X	X r				X	X		X	X s
HbA1c	X						X		X	X s

Phase	Screening Phase	Double-Blind Treatment Phase a								End-of-Study/Follow-up b
Visit Number	1	2	3	4	5	6	7	8	9	10
Study Day	-28	1	7	14	28	42	84	126	168	182
Study Week	-4	1	1	2	4	6	12	18	24	25-26
Visit Window (days)			±3	±3	±3	±4	±7	±7	±7	7 to 14 days after the last dose
Clinic (C), Phone (P)	C	C	P c	C	C	C	C	C	C	C
Safety Assessments (continued)										
Lipid panel	X	X r				X	X		X	X s
Vital signs	X	X		X	X	X	X	X	X	X
TSH and FT 4 l	X						X		X	
Weight	X	X				X	X		X	X s
Waist circumference	X	X				X	X		X	
ECG	X	X				X			X	X s
ASEX		X					X		X	X s
ESRS-A				X	X	X	X		X	X s
C-SSRS	X	X		X	X	X	X	X	X	X
PWC										X
AE	Continuous									
Concomitant medications	Continuous									
PK, Biomarkers and PGx										
Salivary cortisol (pm and am) l		X		X		X	X		X	

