**Table 2: Dose Description**

Dose Level	Capsules
20-mg JNJ-42847922	20 mg and placebo
40-mg JNJ-42847922	20 mg and 20 mg
50-mg Quetiapine XR	50 mg and placebo
150-mg Quetiapine XR	150 mg and placebo
300-mg Quetiapine XR	150 mg and 150 mg

All subjects randomized to JNJ-42847922 will receive 20 mg as a starting dose. Subjects randomized to quetiapine XR will receive 50 mg once daily for 2 days, followed by an increase to 150 mg once daily on Day 3, as per prescribing guidelines in the product label. After the initial dosing period, dose adjustments may be made starting with the first scheduled clinic visit (Day 14). The first dose adjustment must be upwards. Subsequent adjustments may be made upwards or downwards within the study dose ranges (20 or 40 mg for subjects randomized to JNJ-42847922 or 150 or 300 mg for subjects randomized to quetiapine XR) if necessary, depending upon the investigator's assessment of the subject's clinical response and tolerability.

Adjustments of dose should only be made after a clinic visit (if needed may be an unscheduled visit) and assessment of efficacy and tolerability of the medication.

Subjects for whom tolerability at the lowest dose is either unacceptable or cannot be appropriately managed should be withdrawn from the study, and the AE recorded as a reason for discontinuation. For subjects on the highest doses, if there is a lack of response after a clinically appropriate treatment time, the investigator should consider discontinuing the subject due to lack of efficacy.

Subjects will administer the assigned study drug once daily at bedtime, approximately 3 hours after the last meal, from Day 1 to Day 167. Subjects are required to record the administration of study drug or any missed doses in subject diaries, which will be checked at each scheduled visit. The capsules must be swallowed whole and not chewed, divided, dissolved or crushed (see [Table 3](#)) for description of interventions.

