2.6. Definition of Subgroups

Subgroup	Definition
Baseline ISI score	
 • ≥ 15 • < 15 using the randomization stratification factor as entered into IWRS; this will also be used in the analyses as the baseline insomnia status
Baseline MADRS total score	
 • \leq median • $>$ median
MDD subtype based on SCID-CT	
 • With anxious distress • Without anxious distress based on the Structured Clinical Interview for Diagnostic and Statistical Manual of Mental Disorders-Fifth Edition (DSM-5) Axis I Disorders – Clinical Trials Version (SCID-CT)
Sex	
 • Male

Subgroup	Definition
	
 Female Undifferentiated
Age Group	
 18-34 35-54 55-64 65-70
Sex and Age Group	
 Adults (18-64) male, Elderly (≥ 65) male, Adults (18-64) female, Elderly (≥ 65) female
MDD with Anxiety based on HAMA-A	
 Yes, defined as baseline HAM-A total score ≥ 18 No, defined as baseline HAM-A total score < 18
Class of antidepressant study medication	
 SNRI SSRI
Final dose	
 Seltorexant 20mg Seltorexant 40mg Quetiapine XR 150mg Quetiapine XR 300mg
Number of antidepressants of sufficient dose and with inadequate response taken for at least 4 weeks during the current episode	
 1 2 or more based on the Massachusetts General Hospital-Antidepressant Treatment Response Questionnaire (MGH-ATRQ)
Number of major depressive episodes in lifetime, including current episode	
 ≤ 3 > 3
Prior medication use of adjunctive antipsychotics	
 Yes No
Prior medication use of benzodiazepines	
 Yes No
Baseline body mass index (BMI)	
 underweight $< 18.5 \text{ kg/m}^2$ normal $18.5 - < 25 \text{ kg/m}^2$ overweight $25 - < 30 \text{ kg/m}^2$ obese $\geq 30 \text{ kg/m}^2$
Race	
 categories as collected on eCRF
Ethnicity	
 categories as collected on eCRF

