5.2.3.1. Subgroup Analyses

Descriptive statistics (number of discontinuations, number of censored subjects, median, 25th and 75th percentile, if estimable) will be provided for the primary efficacy endpoint (time to all-cause discontinuation of study drug) by the subgroups identified in Section 2.6. Subgroup analysis will be performed using the Cox proportional hazards model. The model will include terms for treatment, subgroup and treatment-by-subgroup. One subgroup at a time will be included in the model. A forest plot with the corresponding hazard ratios and 80% CI will be presented for the subgroups. If there are insufficient numbers in the subgroups to draw meaningful conclusions, the subgroup analysis will not be performed. The Kaplan-Meier plots will be provided for the subgroups with baseline ISI ≥ 15 and baseline ISI < 15 .

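### Time to discontinuation is summarised by final dose, a level fixed at the moment of stopping, so the table cannot be read as a dose effect

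*SAP*

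**What the plan says.** SAP 2.6 lists final dose as a subgroup with four levels: seltorexant (JNJ-42847922) 20 mg and 40 mg, "Quetiapine XR 150mg", and quetiapine XR 300 mg. SAP 4.4 supplies the definition: "The final dose is the last non-zero dose received during the double-blind phase". SAP 5.2.3.1 asks for the number of discontinuations, number censored, median and quartiles of the primary endpoint "by the subgroups identified in Section 2.6". It adds a Cox model with treatment, subgroup and their interaction, and a forest plot. SAP 5.2.1 measures the endpoint from first dose to last dose.

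Protocol section 6 starts all JNJ-42847922 subjects on 20 mg. Quetiapine XR subjects "will receive 50 mg once daily for 2 days, followed by an increase to 150 mg once daily on Day 3". Dose changes may begin only with the Day 14 clinic visit, and "The first dose adjustment must be upwards"; later changes may go either way. They depend on the investigator's view of response and tolerability. The Time and Events Schedule gives Visit 4 a window of 3 days either side.

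**The concern.** The dose level is read off at the last dose, which is also when the event occurs. A stop before the Week 2 visit can never count in a higher-dose row. Each later visit at which a dose can be raised gives the higher row more time in which, by construction, nobody in it has stopped. This is immortal-time bias. The SAP has no landmark and no time-varying dose for this summary.

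There is a second, separate gap. A quetiapine subject who stops after one or two doses has a final dose of 50 mg, which none of the four levels covers, and the SAP gives no rule for that case. A JNJ-42847922 subject who stops on the same day stays in the 20 mg row.

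At stake is how the table is read: a difference in persistence between dose rows would look like information about dose when it need not be.

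**Working it through.** **Inputs.** The plan gives no figure for this table, so the discontinuation rates come from its sample-size section (protocol 11.2, SAP 1.4): 50% on quetiapine XR and a hazard ratio of 0.415. These imply 1 − 0.5^0.415 = 25% on JNJ-42847922. As a check, events = 25 + 12.5 = 37.5, and √(37.5/4) × |ln 0.415| − 1.2816 = 1.41, which gives power of 92.1%. The plan states approximately 92%.

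Assumptions: constant hazard to Day 168; dose has no effect on stopping; increases possible at Days 14, 28, 42, 84 and 126. The documents give no titration rates, so the proportion raised per visit, u, is varied.

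**Formula.** With S(t) = 0.5^(t/168), S at Days 14, 28, 42, 84, 126 and 168 is 0.944, 0.891, 0.841, 0.707, 0.595 and 0.500. With no reductions, the proportion still on the lower dose after k visits is (1 − u)^k. Then:

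- stops in the lower row = Σ [S(t_k) − S(t_k+1)] × (1 − u)^k, k = 0 to 5
- completers in the lower row = 0.5 × (1 − u)^5

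**One case in full, u = 30%.** Lower-row stops: 0.0561 + 0.0371 + 0.0245 + 0.0459 + 0.0270 + 0.0159 = 0.2065. Lower-row completers: 0.5 × 0.168 = 0.0840. Discontinued: 0.2065 / 0.2905 = 71%. Higher row: (0.5 − 0.2065) / (1 − 0.2905) = 0.2935 / 0.7095 = 41%.

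**All cases, percent discontinued, lower row vs higher row:**

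| Per visit | 50% arm | 25% arm |
|---|---|---|
| 15% up | 59 vs 39 | 32 vs 18 |
| 30% up | 71 vs 41 | 43 vs 20 |
| 50% up | 89 vs 44 | 70 vs 21 |
| 30% up, 30% down | 54 vs 45 | 28 vs 22 |

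The true difference is zero in every line.

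**Titration linked to outcome (50% arm, dose still without effect).** Let half the subjects be poor responders with a higher hazard who are raised more often (assumption).

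- Hazard 2 times, raised 50% vs 10% per visit: 54% lower row vs 47% higher row.
- Hazard 3 times, raised 70% vs 10%: 47% vs 52%.
- Hazard 6 times, raised 80% vs 10%: 40% vs 56%.

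The gap shrinks and then reverses.

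**The 50 mg gap.** Stops by Day 2: 1 − 0.5^(2/168) = 0.8%, or 0.4 of 50 subjects.

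**Landmark check (no dose effect, titration unrelated to outcome).** Among subjects still on drug at Day 14, both rows give 1 − 0.5/0.944 = 47% in the 50% arm and 23% in the 25% arm. At Day 42 both rows give about 41% and 19%. The artefact disappears.

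**The case against.** The strongest reply is that the size and direction above depend on titration rates that the documents do not give. The steepest gaps need half of the lower-dose subjects raised at every visit and nobody reduced, although the protocol allows reductions. This stands: the figures are illustrations.

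A reader might infer that the table must show the higher dose of both drugs as better tolerated whatever the truth. The documents do not support that. Titration follows response and tolerability, and protocol section 6 asks investigators to consider stopping non-responders on the highest doses, which places those stops in the higher row. The endpoint is also all-cause, so tolerability is only one part of it.

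A reader might also infer that the missing 50 mg level makes the lower doses look worse. It works the other way: leaving those subjects out takes events from the 150 mg row. Nor do the documents say that such subjects are excluded; they simply match no level.

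On the stakes, no objective compares doses. The protocol introduction assigns the placebo-controlled study of 10, 20 and 40 mg to a separate trial. Its remark that these data will guide phase 3 comes in the rationale for the comparator, and says nothing of dose choice. SAP 6.1 has its own adverse-event table by most recent dose. All of this lowers the weight of the point.

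The SAP's provision to drop a subgroup analysis when numbers are insufficient does not help. At 30% raised per visit, 29% of a 50%-discontinuation arm ends on the lower dose and 71% on the higher, so both rows are populated.

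**Conclusion.** The concern holds in a limited form. A summary of time to discontinuation by last dose taken is grouped by something that depends on the outcome, and it cannot be read as a dose effect. With no dose effect, titration unrelated to outcome and no reductions, a 50%-discontinuation arm shows a gap of about 20 to 45 percentage points between rows (59 − 39 to 89 − 44) for 15% to 50% raised per visit. Equal 30% increases and reductions leave about 9 points (54 − 45). The direction is not guaranteed, because titration driven by poor response can cancel or reverse it. The 50 mg gap is real but minor: 0.4 of 50 subjects at constant hazard, more if early stopping is concentrated in the first days.

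The primary treatment comparison does not use final dose and is unaffected. The point should be fixed because the summary is prespecified and the correction is cheap.

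**What to change.** In SAP 5.2.3.1, remove final dose from the primary-endpoint subgroup summary, the Cox model and the forest plot. Changing only the descriptive table would leave the same bias in the model. Each final-dose level also belongs to a single arm, so a treatment-by-subgroup term has nothing to estimate there.

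In its place, give a descriptive summary within each arm: among subjects still on drug just after the Week 2 visit, time to discontinuation from that visit by the dose then in effect. It may be repeated at Week 6, or supplemented by a model with dose as a time-varying covariate. Label it non-causal, because a landmark removes the immortal time but not the confounding from the reasons for titration. Report stops before the landmark once per arm, with the dose at stop.

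In SAP 2.6, label the lower quetiapine level as 150 mg including the initial 50 mg, for tabulation only.

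The cost is a few SAP sentences; SAP 4.4 and 5.2.3 already rely on dose and date records. The downside is that stops before the landmark leave the dose-wise summary. In a 50% arm at constant hazard that is about 6% of subjects at Day 14 (2.8 of 50). At Day 42 it is about 16% (8 of 50, or 32% of that arm's 25 events), which is why Week 2 is the better main landmark.

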4.5. Protocol Deviations

In general, the following list of major protocol deviations may have the potential to impact subjects' rights, safety or well-being, or the integrity and/or result of the clinical study. Subjects with major protocol deviations will be identified prior to database lock and the number and percentage of subjects with major protocol deviations will be summarized by category using the full analysis set.

- Developed withdrawal criteria but not withdrawn
- Entered but did not satisfy criteria
- Received a disallowed concomitant treatment
- Received wrong treatment or incorrect dose
- Other

More categories may be included depending on the nature of the protocol deviation. A subject may be counted in more than one deviation category.

A by-subject listing showing the specific major protocol deviations will also be provided.

A summary of the number of subjects in the safety analysis set not meeting each inclusion/exclusion criterion will be presented.

4.6. Prior and Concomitant Medications

Prior and concomitant medications will be coded using the World Health Organization Drug Dictionary (WHO-DD). Prior medications are defined as any therapy used before the day of first dose (partial or complete) of study agent. Concomitant medications are defined as any therapy used on or after the same day as the first dose of study agent, including those that started before and continue after the first dose of study agent.

If the medication start date is recorded as partial or completely missing, then the medication will be considered to be concomitant unless it is known to be prior to the first administration of study drug based on partial start date or stop date or the CRF indicates that the medication was taken

prior (prior medication flag=Yes) (see Section 2.10 for detailed classification of prior and concomitant medications).

Prior medications will be summarized by treatment group and standardized medication name for the safety analysis set. The proportion of subjects who receive each prior medication will be summarized as well as the proportion of subjects who receive at least one prior medication. In addition, the number and percent of subjects who receive antidepressant medications prior to the study will be summarized.

Summaries of concomitant medications (other than antidepressant medications) will be presented by treatment group and base preferred term for the safety analysis set, for those medications used during the double-blind phase and for those used during the follow-up phase separately. Definitions for concomitant medications used during the double-blind phase and those used during the follow-up phase are provided in Section 2.10.2 and 2.10.3, respectively. The proportion of subjects who receive each concomitant medication will be summarized as well as the proportion of subjects who receive at least one concomitant medication.

In addition, summary tables of the antidepressant concomitant medications received during the study will be presented by treatment group, for those medications used during the double-blind phase and for those used during the follow-up phase separately.

A by-subject listing of all prior and concomitant medication will also be provided.

